7.2.3. Laboratory Evaluations of Special Interest

7.2.3.1. Liver-Related Laboratory Evaluations

Liver-related abnormalities after initial study drug dosing will be examined and summarized using the number and percentage of subjects who were reported to have the following laboratory test values for postbaseline measurements:

- AST: (a) > 3 times of the upper limit of reference range (ULN); (b) > 5 x ULN; (c) > 10 x ULN; (d) > 20 x ULN
- ALT: (a) > 3 x ULN; (b) > 5 x ULN; (c) > 10 x ULN; (d) > 20 x ULN
- AST or ALT > 3 x ULN and total bilirubin > 2 x ULN

The summary will include data from all postbaseline visits up to 30 days after the last dose of filgotinib in GLPG0634-CL-205. For individual laboratory tests, subjects will be counted once based on the most severe postbaseline values. For both the composite endpoints of AST or ALT and total bilirubin, subjects will be counted once when the criteria are met at the same postbaseline visit date. The denominator is the number of subjects in the Safety Analysis Set who

have nonmissing postbaseline values of all relevant tests at the same postbaseline visit date. A listing of subjects who met at least 1 of the above criteria will be provided.

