- Complicated herpes zoster infection (with multi-dermatomal, disseminated, ophthalmic, or CNS involvement)
- Evidence of active HCV during the study, as evidenced by HCV RNA positivity
- Evidence of active HBV during the study, as evidenced by HBV DNA positivity
- Unacceptable toxicity, or toxicity that, in the judgment of the investigator, compromises the subject's ability to continue study-specific procedures or is considered to not be in the subject's best interest

- Treatment failure deemed by the investigator as lack of improvement or worsening of the disease symptoms or occurrence of intolerable AEs.
- Subject request to discontinue for any reason
- Subject noncompliance
- Pregnancy during the study (Section 8.8.1.2.1.5 and Appendix 13.8)
- Discontinuation of the study at the request of Galapagos, a regulatory agency or an institutional review board or independent ethics committee (IRB/IEC)
- Subject use of prohibited concurrent therapy *may* trigger study drug discontinuation; consultation should be made with the *medical monitor*.
- Laboratory criteria:

After becoming aware of any of the below described abnormal laboratory changes occurring at any one time, an unscheduled visit (ie sequential visit) should occur to retest within 3 to 5 days (except for creatinine, which should be retested 7-14 days later, unless medically indicated sooner).

- 2 sequential white cell counts <2000 cells/mm³ (SI: $<2.0 \times 10^9$ cells/L)
- 2 sequential neutrophil counts <1000 neutrophils/mm³ (SI: $<1.0 \times 10^9$ cells/L)
- 2 sequential lymphocyte counts <750 lymphocytes/mm³ (SI: $<0.75 \times 10^9$ cells/L)
- 2 sequential hemoglobin <8.0 g/dL (SI: <80 g/L)
- 2 sequential platelet counts $<75,000$ platelets/mm³ (SI: $<75.0 \times 10^9$ cells/L)
- 2 sequential aspartate aminotransferase (AST) or ALT elevations >3 times the upper limit of normal with at least one total Bilirubin value >2 times the upper limit of normal^a;
- 2 sequential AST or ALT elevations >3 times the upper limit of normal accompanied by symptoms consistent with hepatic injury^a;
- 2 sequential AST or ALT elevations >3 times the upper limit of normal accompanied by elevated INR;
- 2 sequential AST or ALT elevations >5 times the upper limit of normal, regardless of total Bilirubin or accompanying symptoms^a;
- 2 sequential values for estimate creatinine clearance <35 mL/min based on the Cockcroft Gault formula^b;

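### The SAP's combined AST/ALT and bilirubin row requires both elevations on one visit date, so it omits a subject whose bilirubin crosses later, after the enzymes have fallen

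*SAP*

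**What the plan says.** SAP 7.2.3.1 gives separate rows for AST and ALT at four multiples of ULN, and one composite row, "AST or ALT > 3 x ULN and total bilirubin > 2 x ULN". The two kinds of row follow different counting rules. For the single tests, "For individual laboratory tests, subjects will be counted once based on the most severe postbaseline values". For the composite, "subjects will be counted once when the criteria are met at the same postbaseline visit date", and the denominator is limited to subjects in the Safety Analysis Set who "have nonmissing postbaseline values of all relevant tests at the same postbaseline visit date". On the data span: "The summary will include data from all postbaseline visits up to 30 days after the last dose of filgotinib in GLPG0634-CL-205". On the listing: "A listing of subjects who met at least 1 of the above criteria will be provided".

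Protocol 8.4.2 has a permanent-discontinuation criterion built on the same two thresholds. It asks for two sequential AST or ALT values above 3 x ULN, "with at least one total Bilirubin value >2 times the upper limit of normal". It does not say on which date, or within what interval, the bilirubin value must fall. For most of the laboratory criteria, including this one, "an unscheduled visit (ie sequential visit) should occur to retest within 3 to 5 days".

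**The concern.** Long-term safety is the primary objective, and this is the only row in SAP 7.2.3.1 that looks at enzymes and bilirubin together. The plan generates repeat samples at which bilirubin may be seen to rise after the enzymes: the retest, the EDV chemistry and the Follow-up chemistry. The SAP admits those values to the summary, but the same-date condition bars pairing them with an earlier enzyme peak.

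Section 7.2.3.1 has no bilirubin-only row. In its counts, a subject with a delayed bilirubin rise therefore looks the same as one with an isolated enzyme rise. For an event this rare, one subject decides whether the report reads none or one. On the literal reading of 8.4.2, the report could show no combined case while a subject had been stopped under the combined criterion.

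**Working it through.** The plan gives no figure for this row, so there is none to reproduce. The check compares the two rules.

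**Do late values fall inside the SAP's span?** SAP 3.5.1 sets the last dose at the Final Visit or EDV date. Protocol 8.7.3 puts the Follow-up Visit 2 weeks (+/- 4 days) later, so at most 14 + 4 = 18 days after the last dose. That is within 30 days. Retests 3 to 5 days after an abnormal on-treatment value are also inside the span.

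**Hypothetical subject A (outside the stopping criterion).** Values are multiples of ULN.

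| Date | ALT | Bilirubin | Both crossed? |
|---|---|---|---|
| Quarterly visit | 6 | 1.6 | No |
| Retest | 2.8 | 2.4 | No |

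The combined row omits this subject. The 8.4.2 combined criterion is not met either, because the second ALT is below 3.

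**Hypothetical subject B (literal reading of 8.4.2).**

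| Date | ALT | Bilirubin | Both crossed? |
|---|---|---|---|
| 1 | 4.0 | 1.2 | No |
| 2 | 3.4 | 1.7 | No |
| 3 | 2.6 | 2.3 | No |

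There are two sequential ALT values above 3 and one bilirubin value above 2, so the criterion is met as written. No single date has both, so the combined row omits the subject.

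**Enumeration.** Code each date as enzymes crossed (yes/no) and bilirubin crossed (yes/no), and list all 4^T patterns over T dates. The open reading of 8.4.2 accepts bilirubin from any date. The narrow reading accepts it only from one of the two sequential enzyme dates.

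| T | Patterns | Meet 8.4.2, open | Of these, not in SAP row | Meet 8.4.2, narrow | Of these, not in SAP row | In SAP row, not 8.4.2 (open) |
|---|---|---|---|---|---|---|
| 2 | 16 | 3 | 0 | 3 | 0 | 4 |
| 3 | 64 | 21 | 2 | 19 | 0 | 18 |
| 4 | 256 | 120 | 13 | 103 | 0 | 68 |

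These are counts of patterns, not probabilities. The narrow reading gives zero by logic: bilirubin crossed on a date when the enzymes are also crossed is a same-date crossing.

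**Effect of pairing across dates.** If bilirubin may fall on any date in the sequence, the omissions of 2 and 13 both become 0. If bilirubin must fall on or after an enzyme date, and all dates lie within the window, they become 1 and 5. With T = 3, the remaining pattern is bilirubin on date 1 only and enzymes on dates 2 and 3. With T = 4, enzyme dates 3-4 leave three patterns (bilirubin on 1, on 2, or on both), dates 2-3 leave one (bilirubin on 1), and dates 2-3-4 leave one (bilirubin on 1). In all of these, bilirubin crosses only before the enzymes.

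**Scale.** Take N = 739 enrolled (Protocol 8.3.1) and assume all are in the denominator. Zero cases gives an exact two-sided 95% upper limit of 1 - 0.025^(1/739) = 0.50%. One case gives 1/739 = 0.14%, with exact 95% CI 0.003% to 0.75%. The row is presented by two groups (SAP 3.2), so each actual denominator is smaller than 739.

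**The case against.** A reader might infer that subjects stopped under the protocol's liver criterion will generally drop out of the liver summary. The documents do not support that. The bilirubin condition is attached to the two sequential enzyme elevations and can fairly be read as one of those two samples. AST, ALT and bilirubin belong to one chemistry panel done at every visit (Protocol 8.8.1.2.2), although the content of an unscheduled retest is not stated. On that reading, with the panel drawn together, every stopped subject is counted. A miss needs the open reading and bilirubin raised only on a date without raised enzymes, or a bilirubin value drawn without them. A value first seen after the drug was stopped cannot have triggered the stop.

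A reader might also infer that such a subject disappears from the report, or that this row is the only tabulated liver signal. Neither is so. AST and ALT are tabulated separately, SAP 7.2.2.3 tabulates graded abnormalities by laboratory test, SAP 7.1.6.1 tabulates serious events and events leading to discontinuation, and the listing includes anyone who met a single criterion.

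Nor can the row be said only to undercount. It needs no repeat value, so measured against 8.4.2 it is wider in that respect, as the last column of the enumeration shows.

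Finally, the row is a descriptive summary and need not mirror the stopping criterion, and the documents supply no pairing window. Both points are fair. They limit the size of the concern but do not answer it: on either reading of 8.4.2, the combined row omits a subject like A.

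**Conclusion.** The concern holds in a limited form. The same-date condition makes the combined row insensitive to bilirubin that crosses after the enzymes have fallen, although the SAP already includes the samples that would show it. That holds on either reading of 8.4.2. Whether a subject stopped under 8.4.2 can also be absent depends on a point the protocol leaves open, namely which bilirubin value counts.

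The omission concerns the combined row and, where the tests never share a date, its denominator. The single-test rows and the listing still show the subject. The documents do not allow the number missed to be estimated. The 739-subject figures show only what one case would mean, and they assume that every enrolled subject is in the denominator. This is a cheap improvement to a summary that serves the primary objective, not a flaw that undermines the safety analysis.

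**What to change.** In SAP 7.2.3.1:

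1. Keep the same-date row and its denominator.
2. Add a second row counting subjects with total bilirubin above 2 x ULN on or after the date of an AST or ALT above 3 x ULN, within a pre-specified window. Thirty days is one option, not a figure taken from the documents as a pairing rule. It matches the SAP's post-dose span, covers the 3 to 5 day retest and the 18-day maximum from EDV to Follow-up, and is shorter than the interval between quarterly visits (84 days nominal; 84 - 14 = 70 days at the extremes of the +/- 1 week visit windows).
3. State that the new row uses all scheduled, unscheduled, EDV and Follow-up values in the existing span. Its denominator should be subjects with at least one postbaseline value of each test.
4. Flag in the listing every subject who met the Protocol 8.4.2 combined criterion. On the literal reading, the flag also covers the patterns in which bilirubin crosses only before the enzymes, which the new row does not count.
5. Reconcile the SAP with 8.4.2 on which bilirubin value counts. This is a request for consistency and takes no position on the clinical criterion.

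The cost is a few sentences and a little programming. The added row may include some coincidental pairings, which is why the same-date row should stay beside it.

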7.2.3.2. Complete Blood Count-Related Laboratory Evaluations

Complete blood count (CBC)-related abnormalities such as anemia, leucopenia, neutropenia, lymphopenia, and thrombocytopenia after initial study drug dosing will be examined and summarized using the number and percentage of subjects who were reported to have the following laboratory test values for postbaseline measurements:

- Hemoglobin: (a) any postbaseline worsening CTCAE grade from filgotinib baseline; (b) filgotinib baseline value of less than Grade 3 and increase to Grade 3 or higher at worst postbaseline; (c) filgotinib baseline value of less than Grade 3 and increase to Grade 4 at worst postbaseline
- WBC count: (a) any postbaseline worsening CTCAE grade from filgotinib baseline; (b) filgotinib baseline value of less than Grade 3 and increase to Grade 3 or higher at worst postbaseline; (c) filgotinib baseline value of less than Grade 3 and increase to Grade 4 at worst postbaseline
- Absolute neutrophil count: (a) any postbaseline worsening CTCAE grade from filgotinib baseline; (b) filgotinib baseline value of less than Grade 3 and increase to Grade 3 or higher at worst postbaseline; (c) filgotinib baseline value of less than Grade 3 and increase to Grade 4 at worst postbaseline
- Lymphocyte count: (a) any postbaseline worsening CTCAE grade from filgotinib baseline; (b) filgotinib baseline value of less than Grade 3 and increase to Grade 3 or higher at worst postbaseline; (c) filgotinib baseline value of less than Grade 3 and increase to Grade 4 at worst postbaseline
- Platelet count: (a) any postbaseline worsening CTCAE grade from filgotinib baseline; (b) filgotinib baseline value of less than Grade 3 and increase to Grade 3 or higher at worst postbaseline; (c) filgotinib baseline value of less than Grade 3 and increase to Grade 4 at worst postbaseline

The summary will include data from all postbaseline visits up to 30 days after the last dose of filgotinib.

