7.2.2.1. Treatment-Emergent Laboratory Abnormalities

Treatment-emergent laboratory abnormalities are defined as values that increase at least 1 toxicity grade from filgotinib baseline at any postbaseline time point, up to and including the date of last dose of filgotinib plus 30 days for subjects who permanently discontinued filgotinib in GLPG0634-CL-205, or the last available date in the database snapshot for subjects who were still on treatment at the time of an interim analysis.

If the relevant filgotinib baseline laboratory value is missing, any abnormality of at least Grade 1 observed within the time frame specified above will be considered treatment emergent.

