7.2.2.2. Treatment-Emergent Marked Laboratory Abnormalities

Treatment-emergent marked laboratory abnormalities are defined as values that increase from filgotinib baseline by at least 3 toxicity grades at any postbaseline time point, up to and including the date of the last dose of filgotinib plus 30 days for subjects who permanently discontinued filgotinib in GLPG0634-CL-205 or the last available date in the database snapshot for subjects who were still on treatment at the time of an interim analysis.

If the relevant filgotinib baseline laboratory value is missing, any Grade 3 or higher values observed within the time frame specified above will be considered treatment-emergent marked abnormalities.

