7.2.2.3. Summaries of Laboratory Abnormalities

Laboratory data that are categorical will be summarized using the number and percentage of subjects in the study with the given response at filgotinib baseline and each scheduled postbaseline visit.

The following summaries (number and percentage of subjects) for treatment-emergent laboratory abnormalities will be provided by lab test and treatment group; subjects will be categorized according to the most severe postbaseline abnormality grade for a given laboratory test:

- Graded laboratory abnormalities
- Grade 3 or higher laboratory abnormalities
- Marked laboratory abnormalities

For all summaries of laboratory abnormalities, the denominator is the number of subjects with nonmissing postbaseline values up to 30 days after last dosing date of filgotinib in GLPG0634-CL-205.

A by-subject listing of treatment-emergent Grade 3 or higher laboratory abnormalities and marked laboratory abnormalities will be provided separately by subject ID number and visit in chronological order. These listings will include all test results that were collected throughout the study for the laboratory test of interest, with all applicable severity grades or abnormal flags displayed.

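### SAP 7.2.3.2: a subject who worsens from Grade 3 to Grade 4 on a blood count is in neither severe-cytopenia row, so those rows can only equal or understate the treatment-emergent counts in 7.2.2.3

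*SAP*

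**What the plan says.** SAP 7.2.3.2 is the special-interest table for blood counts. For each of five tests it lists three criteria, called rows here:

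- Row (a) takes every subject whose CTCAE grade rises at all above the filgotinib baseline.
- Row (b) takes subjects who start under Grade 3 and whose worst later value is at Grade 3 or above.
- Row (c), the Grade 4 row, reads: "filgotinib baseline value of less than Grade 3 and increase to Grade 4 at worst postbaseline".

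The data window runs to 30 days after the last filgotinib dose. The section states no denominator and no rule for a missing baseline.

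SAP 7.2.2 sets the general rules for graded laboratory results over the same window:

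- Section 7.2.2.1 defines treatment-emergent abnormalities as "values that increase at least 1 toxicity grade from filgotinib baseline at any postbaseline time point", with no upper limit on the baseline grade. It also covers absent baselines: "If the relevant filgotinib baseline laboratory value is missing, any abnormality of at least Grade 1 observed" in the window counts as treatment-emergent.
- Section 7.2.2.2 defines marked abnormalities as "values that increase from filgotinib baseline by at least 3 toxicity grades at any postbaseline time point". With a missing baseline, any Grade 3 or higher value counts as marked.
- Section 7.2.2.3 summarizes treatment-emergent abnormalities, including a Grade 3 or higher summary, and "subjects will be categorized according to the most severe postbaseline abnormality grade for a given laboratory test". Its denominator is subjects with a postbaseline value in the window.

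**The concern.** The baseline limit does useful work in row (b): it keeps out a subject who starts and stays at Grade 3. In row (c) it has no such function, because any subject who starts below Grade 4 and reaches Grade 4 has worsened. Its effect there is to remove the subject who goes from Grade 3 to Grade 4, and the same limit removes that subject from (b). In this table the subject is left in row (a), pooled with shifts as small as Grade 0 to Grade 1.

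Long-term safety is the primary objective (Protocol 7.1, SAP 1.1), and this is the table to which a reader interested in cytopenia will turn. Two tables of the same tests over the same window could show different Grade 3 or higher and Grade 4 counts. The special-interest table would be the lower one, and nothing in the SAP explains the difference.

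**Working it through.** The plan states no figure on this point, so there is none to reproduce. The check is to run every pair of filgotinib baseline grade (0 to 4, or missing) and worst postbaseline grade (0 to 4) through the rules as written.

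Let b be the baseline grade and w the worst postbaseline grade.

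- Treatment-emergent (TE, 7.2.2.1): w − b ≥ 1, or b missing and w ≥ 1
- Marked (7.2.2.2): w − b ≥ 3, or b missing and w ≥ 3
- Row (a): w > b
- Row (b): b < 3 and w ≥ 3
- Row (c): b < 3 and w = 4

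With a missing b, rows (a), (b) and (c), read literally, cannot be met. The informative pairs are:

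| b → w | TE | TE, Grade ≥3 | TE, Grade 4 | Marked | (a) | (b) | (c) |
|---|---|---|---|---|---|---|---|
| 0 → 3 | yes | yes | no | yes | yes | yes | no |
| 1 or 2 → 3 | yes | yes | no | no | yes | yes | no |
| 0 or 1 → 4 | yes | yes | yes | yes | yes | yes | yes |
| 2 → 4 | yes | yes | yes | no | yes | yes | yes |
| 3 → 3, 4 → 3, 4 → 4 | no | no | no | no | no | no | no |
| **3 → 4** | **yes** | **yes** | **yes** | no | yes | **no** | **no** |
| missing → 1 or 2 | yes | no | no | no | no | no | no |
| missing → 3 | yes | yes | no | yes | no | no | no |
| missing → 4 | yes | yes | yes | yes | no | no | no |

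**Known baselines.** Of the 25 pairs, 3 → 4 is the only one where row (b) differs from TE Grade ≥3, or row (c) from TE Grade 4. It differs in both. The marked definition does not pick it up either, since 4 − 3 = 1.

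**Direction.** If b < 3 and w ≥ 3, then w − b ≥ 1. Everyone in (b) or (c) is therefore also treatment-emergent, and the counts in (b) and (c) can never exceed those under 7.2.2.3.

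**Missing baselines.** These are a second, smaller mismatch, and they affect row (a) as well. They should be rare. SAP 3.5.2 takes the last available value on or before the first filgotinib dose, and Table 3-5 sets no lower limit on how early that value may be.

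**Size.** The documents do not say how many subjects start at Grade 3. Protocol 8.3.3 sets no numeric blood-count limit for entry to this study, and the core studies' entry limits are not given. What follows is assumption except the 739 enrolled subjects (Protocol 8.3.1). Expected number missing from (b) and (c) for one test = 739 × share at baseline Grade 3 × share of those reaching Grade 4:

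| Share at Grade 3 | 5% reach Grade 4 | 20% | 50% |
|---|---|---|---|
| 0% | 0 | 0 | 0 |
| 0.5% | 0.18 | 0.74 | 1.85 |
| 1% | 0.37 | 1.48 | 3.70 |
| 2% | 0.74 | 2.96 | 7.39 |

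**The case against.** The strongest reply is that two definitions need not be a contradiction. Section 7.2.3.2 does not call rows (b) and (c) treatment-emergent. Read on its own, it asks how many subjects who were not severe at baseline became severe, and how many of those reached Grade 4. That is a coherent quantity, and (c) is a proper subset of (b). This stands as a possible reading. But the SAP does not state it, does not restrict the denominator to subjects below Grade 3 at baseline as that reading would require, and does not warn that the counts may differ from 7.2.2.3.

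The second reply is that nothing disappears. This stands in full. A reader might infer that the SAP hides worsening to Grade 4, and the documents do not support that. The 3 → 4 subject is in row (a), in the graded and the Grade 3 or higher summaries of 7.2.2.3, and in the by-subject listing of treatment-emergent Grade 3 or higher results, which shows all results for the test.

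A reader might also infer that a large share of Grade 4 events goes uncounted. That would need a baseline grade distribution and a Grade 4 event rate, and the documents give neither. Protocol 6.5 reports no decrease in lymphocytes, slightly higher hemoglobin, and mean neutrophil and platelet changes within reference ranges. Group means cannot rule out individual cases, but nothing there points to a sizeable 3 → 4 group.

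Finally, these rows are descriptive, without formal testing (SAP 7.2), and the laboratory discontinuation criteria in Protocol 8.4.2 rest on absolute counts, not on these rows.

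**Conclusion.** The point holds as a definitional fault in two rows of one table, repeated for five tests. Rows (b) and (c) omit worsening from Grade 3 to Grade 4, and also Grade 3 or 4 results with no baseline. Their counts are therefore equal to or below the corresponding 7.2.2.3 counts.

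The size is unknown and probably small. Under the assumed ranges above it runs from 0 to about 7 subjects per test, and that upper end takes the highest value of both assumptions at once. It is exactly zero if no subject starts at Grade 3 or lacks a baseline. Grade 4 counts may themselves be small, in which case one or two omissions would be visible in a row. No test or stopping rule in the plan depends on these rows. The reasons to correct them are agreement between tables and a complete special-interest summary in a study whose primary objective is safety.

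**What to change.** In all five bullets of SAP 7.2.3.2, build the three rows on the 7.2.2.1 definition:

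- (a) an increase of at least 1 grade from filgotinib baseline or, if the baseline is missing, a worst postbaseline grade of 1 or higher;
- (b) subjects meeting (a) whose worst postbaseline grade is 3 or higher;
- (c) subjects meeting (a) whose worst postbaseline grade is 4.

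State the 7.2.2.3 denominator for the table.

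With this text (c) lies within (b) and (b) within (a), subjects who stay at Grade 3 remain excluded, and every pair in the table above agrees with 7.2.2.1 and 7.2.2.3. Narrower repairs do not achieve this. Changing only (c) to a baseline below Grade 4 would put the 3 → 4 subject in (c) but not in (b). Admitting missing baselines to (b) and (c) but not to (a) would break the nesting the other way.

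The cost is SAP wording and one condition in the table program, with no new data. The reported Grade 3 or higher and Grade 4 percentages may become slightly less favourable. If the change comes after SAP finalization, SAP Section 1 already requires it to be documented in the clinical study report.
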